#### Inclusion Criteria:

\*Type II Diabetes or Peripheral Artery disease \*Non-infected deep wounds (Grade 2 in the Wagner Ulcer classification) \*18 years or older

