#### A1. Main Title

COMPARATIVE EFFECTIVENESS OF TWO ACELLULAR MATRICES PRODUCTS (DERMACELL V. INTEGRA) FOR MANAGEMENT OF DEEP DIABETIC FOOT ULCERS - A RANDOMIZED CLINICAL TRIAL

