# Section D: Purpose and Objectives

\*\*\*Please note that this is a reliance protocol\*\*\*

The primary objective of this prospective, randomized trial is to compare the outcomes of DermaCELL with Integra. We assumed that the wounds outcomes (e.g. weekly wound size change, time to heal, time to successful wound granulation) are comparable between DermaCELL and Integra. However, from operation and patient centered outcomes, there may be some noticeable differences. For instance, DermaCELL, thanks to its mesh structure, thin thickness, and no need for hydration, may be easier to apply with shorter time than Integra. The factors are of key importance in operation room (OR) setting and could reduce overall cost of application and needs in using OR resources. Other important outcomes least addressed in prior studies are number of grafts failing, adverse events (e.g. amputation, infection, etc), cost of wound healing treatment, tissue biomechanics, which may lead to recurrence of ulcers (e.g. formation of tissue scarring), and other patient-centered outcomes (e.g. pain, quality of sleeping, wound smelling, etc). For instance, many patients are unhappy with smelling of wounds, which make them embarrassed among their family members like grand kids. Thus reducing wound smelling during activities of daily living is often considered as an important patient centered outcomes.

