# Section F: Design/Procedure

## F1. Design

Select one category that most adequately describes your research:

c) Pilot

Discuss the research design including but not limited to such issues as: probability of group assignment, potential for subject to be randomized to placebo group, use of control subjects, etc.

Thirty four (n=50) patients with diabetes (age 18 years or older) with non-infected deep wounds (grades 2 in the Wagner Ulcer classification) will be randomized into two groups, 17 subjects per group each. The group one will be treated by Meshed DermaCELL and group two will be treated by Meshed Integra template.

The primary outcomes are time to granulation, successful granulation at 8 weeks, and number of failures (e.g. amputation, infection, rejection, re-application) within 8 weeks. Secondary outcomes include time to apply, weekly speed of wound healing after successful granulation and transition to standard wound therapy, success of wound healing at 12 weeks and @16 weeks, cost of wound treatment upto 16weeks (based on patient electronic record), tissue biomechanics after wound healing (e.g. presence of scarring or tissue biomechanics properties leading to increase in shear or pressure post healing), change in skin perfusion (assessed with SPP), change in thermography response, recurrence of ulcers up to 6 months post healing, and other patient centered outcomes including perception of pain, physiological stress response as surrogate of pain (e.g. heart rate variability during dressing change), sleep quality (assessed by PSQI and sensor-based sleep quality index), wound smelling (assessed by Likert scale), and patient perception of benefit (assessed by technology acceptance model, TAM based on perception of benefit and attribute of benefits).

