#### **Exclusion Criteria:**

\*No minors will be consented. \*Active infection \*Gangrene or osteomyelitis \*Major vascular problems (ABI lower than 0.5, or ABI greater than 1.3) \*Unlikely to fully comply with the follow-up protocol (e.g. long distance travel) \*Unable or unwilling to provide informed consent

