#### F2. Procedure

\*\* Reliance protocol \*\* There are a total of 17 study visits.

Medical History: The presence of diabetes will be determined based on American Diabetes Association criteria. This will include: duration and type of diabetes, type of diabetes medication (insulin, oral, combination therapy, diet), previous history of foot ulcers, amputation (toe, foot), lower extremity bypass, lower extremity angioplasty, Coronary artery bypass surgery, cardiac angioplasty, arthritis, liver disease, osteoporosis, malignancy, and bone tumors. We will use the Kaplan co-morbidity index to record disease severity.

Social and Economic Factors: We will evaluate the following factors: marital status, years of education, type of work, tobacco history (pack years, current smoker, current use of chewing tobacco, previous smoker, no tobacco history), drug history (current, previous history, no drug history), and alcohol history. Also we will collect cost information for the subject's treatment up to 6 months after the subject enrolls in the study.

Questionnaires: Quality of Life, Frailty Status, Sleep Quality, Cognitive Status and Device Acceptability: To evaluate functional status we will use well-accepted questionnaires, SF-12 for Quality of Life, Sleep Quality questionnaire (PSQI), MOCA and TSFI for frailty status. In addition, at each visit, we will interview the subject about their concern with their wound and product (e.g. wound drainage, smell, pain, etc.), use of any medications for pain or sleeping, the cost of transport to the clinic, any adverse events (e.g. infection, need to visit a specialist, etc), etc. To see the timeline for each questionnaire, please refer the table included in the ICF attached.

Pain Intensity Assessment (VAS): Researchers will provide a numerical pain scale where subject will report their pain intensity. Researchers will document pain level.

Adverse Event Reporting: Researchers will document and report any study/non study related incident as per institution regulations.

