# Section G: Sample Size/Data Analysis

#### G1. Sample Size

How many subjects (or specimens, or charts) will be used in this study? Local: 50 Worldwide: 50

Please indicate why you chose the sample size proposed:

There is no prior studies to report the major primary outcomes for comparison between DermaCELL and Integra. Based on interviewing our podiatrist who worked with both Integra and DermaCELL, we estimated the time needed to apply each matrices in the OR. We hypothesized that time needed to apply DermallCELL is approximately 3±2 min while the time needed to apply Integra is estimated to be 5±2min (Cohen¿s effect size d=1). Assuming an alpha of 5% and power of 80% and two tailed t-test comparison, 17 subjects per group needed to be recruited to observe a significant difference between two groups from point of view of application time. We anticipate that this sample size should be also sufficient to observe noticeable trend in other outcomes. Based on results of this study, another RCT may be addressed to clinically validate the

observed noticeable trends. Alternatively, the sample size may be increased upon available of budget, approval of sponsor, and noticeable observed trend based on the first 20 recruited subjects (ten per group).

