## G2. Data Analysis

Provide a description of your plan for data analysis. State the types of comparisons you plan (e.g. comparison of means, comparison of proportions, regressions, analysis of variance). Which is the PRIMARY comparison/analysis? How will the analyses proposed relate to the primary purposes of your study?

The primary outcomes are time to granulation, successful granulation at 8 weeks, and number of failures (e.g. amputation, infection, rejection, re-application) within 8 weeks. Mixed models accommodate the longitudinal design; allow for testing differences between groups in patterns over time as well as at specific time points; are consistent with an intention to treat analysis (9), and are valid for data which are missing completely at random or at random (10). Number of failures as well as number of recurrence of ulcers over the 6 month follow-up will be modelled with a generalized linear model using an appropriate count outcome (Poisson, zero-inflated Poisson, negative binomial for overdispersion). Rate ratios comparing intervention arms will be estimated from this model. Appropriate mixed models (linear or generalized linear, for noncontinuous outcomes or logistic regression for binary data) will be used to test the intervention effect for each of the secondary outcomes (e.g. tissue biomechanics, mobility, patient centered outcomes, recurrence of ulcers, etc). A Kaplan-Meier survivorship analysis will be used for estimating time to event for none successful healing probability over time by treatment and the p-value will be calculated using the Log-rank (Mantel-Cox) test. Hazard ratios will be used to indicate the probability of closure at any given point in time for Derma-Cell v. Integra treatment. Univariate logistic regression analyses will be performed to delineate predictive factors of successful granulation at 8 weeks, successful wound healing at 12 weeks, and successful wound healing at 16 weeks. Results will be controlled for potential confounding variables including age, sex, BMI, HbA1c, neuropathy severity, vascular status, frailty, mobility status, and initial wound size. The p-values for weekly % wound area and % wound area reduction through 16 weeks will be calculated using t tests. All p-values, for both the categorical and continuous data, will be calculated using a two-sided alpha of 0.05.

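### As written, the inclusion list admits patients with peripheral artery disease and no diabetes, while the title and F1 name a diabetic population

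*Combined protocol and SAP*

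**What the plan says.** Three places in the combined document describe who is to be studied.

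- **A1, Main Title:** the trial is "FOR MANAGEMENT OF DEEP DIABETIC FOOT ULCERS - A RANDOMIZED CLINICAL TRIAL".
- **F1, Design:** the patients to be randomised are "patients with diabetes (age 18 years or older) with non-infected deep wounds". No diabetes type is specified.
- **Inclusion Criteria:** the disease criterion is "Type II Diabetes or Peripheral Artery disease". The other two criteria are an uninfected deep wound of Wagner grade 2 and adult age.

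Three further places bear on whether the difference is resolved elsewhere.

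- **Exclusion Criteria:** the only vascular limit is an ankle brachial index (ABI) below 0.5 or above 1.3. Absence of diabetes is not listed.
- **F2, Procedure (Medical History):** "The presence of diabetes will be determined based on American Diabetes Association criteria", with duration and type also recorded.
- **G2, Data Analysis:** results are to be controlled for "potential confounding variables including age, sex, BMI, HbA1c, neuropathy severity, vascular status, frailty, mobility status, and initial wound size". No analysis restricted to patients with diabetes is named.

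**The concern.** Eligibility criteria determine whom a trial's result describes. Here the operative list uses *or* where the title and F1 imply that diabetes is always present. A patient with PAD and a qualifying wound, but no diabetes, meets every listed criterion and yet falls outside the population in the title.

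If such patients were randomised, the comparison of the two matrices would be made in a mixed group, and a report under the present title would misdescribe it. Diabetic-only results could still be extracted from the recorded status, but on the text available that analysis would be post hoc. F1 labels the study a pilot, so the consequence is modest, but the conflict sits in a core eligibility line and is cheap to remove.

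**Working it through.** No arithmetic applies. The check is to take the possible patient profiles, assume each has a qualifying wound, adult age and an ABI from 0.5 to 1.3, and ask what each passage says.

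| Profile | Title | F1 | Inclusion list, read literally |
|---|---|---|---|
| Type II diabetes, with or without PAD | in | in | in |
| Other diabetes, with PAD | in | in | in |
| PAD, no diabetes | out | out | **in** |
| Other diabetes, no PAD | in | in | **out** |

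The third row is the point. I looked for anything that would move it to *out*:

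1. **Wound criterion.** It fixes depth, grade and absence of infection. It does not require a diabetic cause, so it does not bring diabetes back in.
2. **Exclusions.** The ABI limits remove the extremes only. A patient with PAD whose ABI lies between 0.5 and 1.3 remains eligible. The other exclusions (minors, infection, gangrene or osteomyelitis, expected poor compliance, no consent) do not concern diabetes.
3. **Medical history in F2.** Diabetes is ascertained by a named standard, but as a baseline item. The sentence does not say that a patient found not to have diabetes is ineligible.
4. **Analysis in G2.** HbA1c and vascular status are listed adjusters, and the list is open because it is introduced by *including*. Adjusting for HbA1c does not restrict the analysis to patients with diabetes, and diabetes status itself is not named.

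Nothing in the available text closes the gap.

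The fourth row is a different matter. F1 is a one-sentence summary, and an inclusion list commonly narrows a summary. It calls for a clarification of diabetes type and is secondary to the third row.

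**The case against.** The best reply is that F1 governs. The inclusion list follows directly under F1, which has already said that the patients have diabetes; the title and Section C are about diabetic foot ulcers; and F2 applies a diagnostic standard for diabetes. If the list operates within that population, no one without diabetes can enter.

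This reading is possible and cannot be excluded. However, the document does not state it, and it leaves the PAD alternative with an odd role: among patients with diabetes, it would matter only for those who are not Type II. It therefore does not remove the need to clarify the wording.

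A second reply is that the supplied form is not the whole protocol. Section C points to a protocol attached in section S, and the text calls itself a reliance protocol. A fuller criteria list may exist there. This stands, and it limits any claim about what screeners would do as well as any claim about the analysis.

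A third reply is that a mixed sample does no harm to a randomised comparison. As regards bias, this is correct: allocation is random whatever the diabetes status. What changes is the population to which the result applies.

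**Conclusion.** The mismatch between the inclusion list and the title and F1 is certain on the supplied text, and it should be corrected. Its practical effect is conditional. It depends on the list being applied literally and on patients with PAD and no diabetes presenting with eligible wounds. The document gives no expected share of such patients, so no magnitude can be computed, and the effect is zero if F1 governs in practice.

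A reader might infer more than this, and the document does not support it:

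- *That patients without diabetes will be enrolled.* The wording permits it; nothing shows that it is intended or would happen.
- *That the treatment comparison would be biased.* Randomisation protects it; only the population described is at issue.
- *That power is lost.* Any such figure would need an assumed number of patients without diabetes, for which there is no basis in the document.
- *That leaving out Type 1 patients without PAD is a second contradiction of equal weight.* It may be ordinary narrowing of a summary sentence.

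**What to change.** Reconcile the title, F1 and the Inclusion Criteria, and any list in the attached protocol, so that they state one population. The document does not show which is intended, so the choice is the investigators'.

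- **If diabetes is required:** make it an entry criterion in the Inclusion Criteria, so that PAD does not qualify a patient on its own, and state which diabetes types are eligible. F1 needs a change only if the type is to be restricted. The cost is wording, and a somewhat smaller recruitment pool if patients with PAD alone would otherwise have been recruited.
- **If patients without diabetes are intended:** say so in the title and F1, and pre-specify in G2 one sensitivity analysis restricted to patients with diabetes, using the status that F2 already records. Keep all randomised patients in the primary analysis, in line with the intention-to-treat aim in G2. The cost is wording and one extra analysis, with no new data collection.

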#### **Exclusion Criteria:**

\*No minors will be consented. \*Active infection \*Gangrene or osteomyelitis \*Major vascular problems (ABI lower than 0.5, or ABI greater than 1.3) \*Unlikely to fully comply with the follow-up protocol (e.g. long distance travel) \*Unable or unwilling to provide informed consent

#### F2. Procedure

\*\* Reliance protocol \*\* There are a total of 17 study visits.

Medical History: The presence of diabetes will be determined based on American Diabetes Association criteria. This will include: duration and type of diabetes, type of diabetes medication (insulin, oral, combination therapy, diet), previous history of foot ulcers, amputation (toe, foot), lower extremity bypass, lower extremity angioplasty, Coronary artery bypass surgery, cardiac angioplasty, arthritis, liver disease, osteoporosis, malignancy, and bone tumors. We will use the Kaplan co-morbidity index to record disease severity.

Social and Economic Factors: We will evaluate the following factors: marital status, years of education, type of work, tobacco history (pack years, current smoker, current use of chewing tobacco, previous smoker, no tobacco history), drug history (current, previous history, no drug history), and alcohol history. Also we will collect cost information for the subject's treatment up to 6 months after the subject enrolls in the study.

Questionnaires: Quality of Life, Frailty Status, Sleep Quality, Cognitive Status and Device Acceptability: To evaluate functional status we will use well-accepted questionnaires, SF-12 for Quality of Life, Sleep Quality questionnaire (PSQI), MOCA and TSFI for frailty status. In addition, at each visit, we will interview the subject about their concern with their wound and product (e.g. wound drainage, smell, pain, etc.), use of any medications for pain or sleeping, the cost of transport to the clinic, any adverse events (e.g. infection, need to visit a specialist, etc), etc. To see the timeline for each questionnaire, please refer the table included in the ICF attached.

Pain Intensity Assessment (VAS): Researchers will provide a numerical pain scale where subject will report their pain intensity. Researchers will document pain level.

Adverse Event Reporting: Researchers will document and report any study/non study related incident as per institution regulations.

Device Acceptability Questionnaire: The subject will be handed a questionnaire to evaluate the study device and provide feedback to the research team. We will be asking about level of satisfaction with the product. These may be questions about the time spent to apply the product, the level of comfort, appearance of the product, the appearance of the healed wound (e.g. presence of scarring), ease of walking or standing with the product and after healing, etc.

Matrix Application: During the subject's wound treatment (either in OR or outpatient clinic), the physician will apply the dermal matrix from the group they were placed. The researchers will write down the duration needed for full application of the product. For accurate estimation of time needed for preparation and application, the whole process may be video-recorded for offline estimate of each time.

Vascular Assessment: We will assess perfusion of the macro-circulation with arterial Doppler studies and micro-circulation with Skin Perfusion Pressure measurements. Ankle Brachial Index (ABI) will be measured on both extremities. We will also use the SensiLase system (Väsamed) to measure Skin Perfusion Pressure (SPP) in mmHg. Additionally, we may use the LUNA or SPY Device for Indocyanine Green Fluorescence Imaging. For this purpose a fluorescent agent may be injected into the subject's body to allow us observe the blood circulation to the wound. Indocyanine Green Fluorescence Imaging (SPY or Luna) may be performed based on the medical judgment of the physician. Highly qualified medical/clinical staff will perform this measurement. If so, measurement will take place only during baseline and treatment day.

Wound Photo: At every visit, the Medical/Researcher using a standard digital camera will take a digital photo of the wound. We will ask the subject's permission to take photos/video.

Wound Assessment: Evaluations will be based on data collected from wound assessments and photographs. We use acetate tracings and digital photos. Additionally, we will use thermal imaging to track inflammation.

Thermal Image: A thermal camera will be used to obtain an image of the wound and observe swelling.

Wifi Wound Classification: Podiatrist or vascular surgeon will evaluate the health and wellness of the subject's feet in compliance of standard of care

Granulation Assessment: The physician will be looking at how the wound heals. Specifically, they will look at the reddish tissue developing on the wound. A digital photograph will be taken and comments made by the physician will be recorded.

Wound Care: The physician will schedule regular visits after the surgery to provide care to the wound as according to standard of care

Dressing Change: Medical and/or clinical staff will change the subject's dressing weekly or as needed.

Peripheral Neuropathy: We will use Vibration Perception Threshold (VPT) Testing to quantify neuropathy severity. VPT will be evaluated at the distal great toe and 5th metatarsal head using a Biothesiometer.

Upper Extremity Assessment: Investigators will measure the subject's arm motion using wearable sensors (LegSys). One sensor will be placed around the wrist and elbow. While being at a comfortable position, they will be asked to flex and extend their arm for 20 s at a fast speed. We will ask to repeat this task but counting backwards (dual task).

Optional Assessments ¿ These may occur at any visit. However, they do not need to be performed.

Physical Exam: The researchers will place 5 sensors named Legsys and Balanses (one on lower back, 2 on each upper thigh, and 2 on each shin) attached with elastic straps to test balance and record your walking patterns. Researchers will ensure that the straps are not too tight to avoid poor circulation

Physical activity: The researchers will provide you with a small sensor (Pamsys) that will be measuring physical activity for 48 hrs. It will record number of steps taken, duration of sitting, standing, walking, and lying. At the end of the visit, the subject will be given the sensor, which will be worn, around the neck. Researchers will provide a pre-paid envelope where they may place the device and send it back to the investigating team after 48 hrs

Heart Rate Monitoring: A comfortable chest worn sensor (Zephyr BioHarness, Medtronic or BioStamp RC, MC10) will be used to measure physiological signs such as heart rate, skin temperature, and physical activity. This device will be comfortable placed on the chest attached either with 2 electrodes or with elastic straps if the subject has sensitive skin. Researchers will attach this device on the subject for the duration of the visit or during 24 hours

The description of every visit is below. Screening/Baseline Visit \*duration of visit 90 minutes This visit will take place at Baylor St. Lukes Medical Center during your surgery day. The researchers will perform as described above: Medical History, Questionnaires (Pain, Social Factors, and Quality of Life, Sleep Quality, Cognitive Assessment, Frailty), Matrix application, Upper Extremity Test, Peripheral Neuropathy, Thermal Image, Vascular Assessment, Wound Assessment, Wifi Wound Classification, and Wound photo.

Visit 1, One Week Later \*duration 50 minutes This visit will take place at Baylor Clinic for a regular follow up appointment. The researchers will perform as described above: Pain Questionnaire, Adverse Event Reporting, Dressing Change, Wound Photo, and Wound Care.

Visit 2, Two Weeks Later \*duration 70 min This visit will take place at Baylor Clinic for a regular follow up appointment. The researchers will perform as described above: Adverse Event Reporting, Wound Assessment, Thermal Image, Dressing Change, Wound Photo, and Wound Care.

Visit 3, Three Weeks Later \*duration 50 min This visit will take place at Baylor Clinic for a regular follow up appointment. The researchers will perform as described above: Adverse Event Reporting, Dressing Change, Wound Photo, and Wound Care.

Visit 4, Four Weeks Later \*duration 70 min This visit will take place at Baylor Clinic for a regular follow up appointment.

The researchers will perform as described above: Pain Questionnaire, Adverse Event Reporting, Sleep Quality Questionnaire, Wound Assessment, Dressing Change, Wound Photo, Thermal Image, and Wound Care.

Visit 5, Five Weeks Later \*duration 70 min This visit will take place at Baylor Clinic for a regular follow up appointment. The researchers will perform as described above: Adverse Event Reporting, Dressing Change, Wound Photo, Granulation Assessment, and Wound Care.

Visit 6, Six Weeks Later \*duration 70 min This visit will take place at Baylor Clinic for a regular follow up appointment. The researchers will perform as described above: Adverse Event Reporting, Dressing Change, Thermal Image, Wound Photo, Granulation Assessment, and Wound Care.

Visit 7, Seven Weeks Later \*duration 70 min This visit will take place at Baylor Clinic for a regular follow up appointment. The researchers will perform as described above: Adverse Event Reporting, Dressing Change, Wound Photo, Granulation Assessment, and Wound Care.

Visit 8, Eight Weeks Later \*duration 90 min This visit will take place at Baylor Clinic for a regular follow up appointment. The researchers will perform as described above: Pain Questionnaire, Sleep Quality Questionnaire, Device Acceptability Questionnaire, Adverse Event Reporting, Dressing Change, Wound Photo, Wound Assessment, Granulation Assessment, Wound Care, Wifi Wound Classification, Thermal Image, and Upper Extremity Assessment.

Visit 9, Nine Weeks Later \*duration 40 min This visit will take place at Baylor Clinic for a study-only follow up appointment. The researchers will perform as described above: Adverse Event Reporting, Dressing Change, Wound Photo.

Visit 10, Ten Weeks Later \*duration 70 min This visit will take place at Baylor Clinic for a regular follow up appointment. The researchers will perform as described above: Adverse Event Reporting, Dressing Change, Thermal Image, Wound Photo, Wound Care, Wound Assessment.

Visit 11, Eleven Weeks Later \*duration 40 min This visit will take place at Baylor Clinic for a study-only follow up appointment. The researchers will perform as described above: Adverse Event Reporting, Dressing Change, Wound Photo.

Visit 12, Twelve Weeks Later \*duration 75 min This visit will take place at Baylor Clinic for a regular follow up appointment. The researchers will perform as described above: Pain Questionnaire, Sleep Quality Questionnaire, Adverse Event Reporting, Dressing Change, Wound Photo, Wound Assessment, Thermal Image, Wound Care.

Visit 13, Thirteen Weeks Later \*duration 40 min This visit will take place at Baylor Clinic for a study-only follow up appointment. The researchers will perform as described above: Adverse Event Reporting, Dressing Change, Wound Photo.

Visit 14, Fourteen Weeks Later \*duration 70 min This visit will take place at Baylor Clinic for a regular follow up appointment. The researchers will perform as described above: Adverse Event Reporting, Dressing Change, Thermal Image, Wound Photo, Wound Care, Wound Assessment.

Visit 15, Fifteen Weeks Later \*duration 40 min This visit will take place at Baylor Clinic for a study-only follow up appointment. The researchers will perform as described above: Adverse Event Reporting, Dressing Change, Wound Photo.

Visit 16, Sixteen Weeks Later \*duration 90 min This visit will take place at Baylor Clinic for a regular follow up appointment. The researchers will perform as described above: Pain Questionnaire, Sleep Quality Questionnaire, Device Acceptability Questionnaire, Adverse Event Reporting, Dressing Change, Wound Photo, Thermal Image, Wound Assessment, Vascular Assessment, Granulation Assessment, Wound Care, Wifi Wound Classification, Upper Extremity Assessment.

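### Time to granulation is a primary outcome, but the visit list schedules no Granulation Assessment before week 5, so granulation in weeks 1 to 4 is not dated

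*Combined protocol and SAP*

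**What the plan says.** Section F1 lists the primary outcomes, and Section G2 repeats them: "The primary outcomes are time to granulation, successful granulation at 8 weeks, and number of failures (e.g. amputation, infection, rejection, re-application) within 8 weeks".

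Section F2 describes Granulation Assessment as a separate item. The physician looks at the reddish tissue in the wound, and "A digital photograph will be taken and comments made by the physician will be recorded". No threshold for success is given. Wound Assessment is a different item: "We use acetate tracings and digital photos", with thermal imaging added. Visit 8 lists both, so the form does not treat one as containing the other.

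The visit list opens with "The description of every visit is below". For the 8-week window it gives:

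- Visit 1: a pain questionnaire plus the Visit 3 items.
- Visit 2: "Adverse Event Reporting, Wound Assessment, Thermal Image, Dressing Change, Wound Photo, and Wound Care".
- Visit 3: "The researchers will perform as described above: Adverse Event Reporting, Dressing Change, Wound Photo, and Wound Care".
- Visit 4: a list ending "Sleep Quality Questionnaire, Wound Assessment, Dressing Change, Wound Photo, Thermal Image, and Wound Care".
- Visit 5, the first to name Granulation Assessment: "Adverse Event Reporting, Dressing Change, Wound Photo, Granulation Assessment, and Wound Care". Visits 6, 7 and 8 name it too.

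After week 8 it appears only at Visit 16. The form gives no reason for starting at week 5.

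On recurrence, Section F1 sets a window of six months from healing, and Section G2 models counts over a six-month follow-up and promises rate ratios. The 17 visits run from baseline to week 16. Only cost collection is stated to continue to six months, and that is counted from enrolment (Section F2).

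**The concern.** The form defines one item for judging granulation and leaves it out of the first four of the eight weekly visits in the primary window. Every event in that half of the window is then first recorded at week 5. A recorded median of 5 weeks could stand for any true value up to 5.

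This matters even if the two products are comparable, as Section D assumes. The study is a pilot whose results may lead to another randomized trial (Section G1), and a median time to granulation is a planning figure for that trial. The date is also needed as the starting point for a secondary outcome in Section F1, the weekly speed of healing once granulation has succeeded.

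The other two primary outcomes are not affected by the start week. Granulation is assessed at week 8, and adverse events are reported at every follow-up visit.

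**Working it through.** **The plan's own figure.** The only sample-size figure is 17 per group in Section G1, for application time (3±2 v 5±2 minutes, d = 1, two-sided 5%, power 80%). An exact two-sample t-test needs 16.71, so 17 per group, with power 80.7%. It reproduces and is untouched by this point. The documents state no figure for granulation.

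**Schedule.** Weeks with Granulation Assessment: 5, 6, 7, 8, 16. Weeks 1 to 8 without it: 1, 2, 3, 4. Of these, weeks 2 and 4 have a Wound Assessment, and all four have a photo and wound care. The first dated interval is therefore (0, 5] weeks rather than (0, 1].

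**Assumptions for size.** Weibull granulation times with median m and shape k of 1.5 or 2, weekly visits, and follow-up cut at week 8. The plan does not state that cut for this outcome, and Section G2 does not name the log-rank test for it.

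**Share granulated by week 4.** F(4) = 1 − 2^(−(4/m)^k). For medians 3 v 4.5 and k = 2, the arms give 70.8% and 42.2%, mean 56.5%. Averaged over both arms and across the two shapes:

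| Medians (weeks) | Granulated by week 4 |
|---|---|
| 2.5 v 4 | 63–67% |
| 3 v 4.5 | 55–57% |
| 4 v 6 | 38–41% |
| 5 v 7 | 28–33% |
| 6 v 8 | 21–27% |

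On average these wounds are dated 1.9 to 2.5 weeks later than weekly assessment would date them.

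**Precision with equal arms.** For grouped proportional hazards, information per subject is the sum over intervals of S(start) × L² × e^(−L) / (1 − e^(−L)), where L is the interval's cumulative hazard and H(t) = ln 2 × (t/m)^k. The standard error of the log hazard ratio is √(2/(n × information)).

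Example, m = 3, k = 2, cut points 5, 6, 7, 8:

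- First interval: L = 0.693 × 25/9 = 1.925, contributing 0.633.
- The other three contribute 0.079, 0.036 and 0.014, total 0.762.
- Cut points 1 to 8 give 0.969.
- Standard-error ratio: √(0.969/0.762) = 1.128.
- At 17 per arm the 95% interval is the estimate times or divided by exp(1.96 × √(2/(17 × 0.969))) = 1.98 with weekly assessment, and exp(1.96 × √(2/(17 × 0.762))) = 2.16 with the week-5 start.

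| Common median | Ratio, shape 1.5 | Ratio, shape 2 |
|---|---|---|
| 2.5 | 1.137 | 1.305 |
| 3 | 1.072 | 1.128 |
| 4 | 1.027 | 1.032 |
| 5 | 1.013 | 1.011 |

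**Log-rank power, weekly dating v week-5 start** (20,000 simulated trials per cell). Loss in percentage points:

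| Medians | Shape 1.5, 17 / 25 per arm | Shape 2, 17 / 25 per arm |
|---|---|---|
| 2.5 v 4 | 4.1 / 6.0 | 9.8 / 7.1 |
| 3 v 4.5 | 2.1 / 3.1 | 4.4 / 4.3 |
| 4 v 6 | 1.0 / 1.1 | 0.7 / 1.2 |
| 5 v 7 | 0.1 / 0.3 | 0.2 / 0.1 |
| 6 v 8 | 0.2 / 0.3 | −0.1 / 0.0 |

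The largest falls are from 71 to 62% at 17 per arm and from 87 to 80% at 25 per arm.

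**Type I error.** With equal arms and medians of 3, 4 or 5 weeks, rejection is about 5 to 6% under either schedule. At 2.5 weeks with shape 2, the week-5 start gives 1.3% at 17 per arm and 2.9% at 25 per arm, which is conservative.

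**Recurrence.** Taking six months as 26 weeks, a wound healed at week h has 16 − h weeks covered by visits: 8/26 = 31% at week 8, 4/26 = 15% at week 12, and 0 at week 16. The payment in Section L (17 × 75 = 1275) agrees with a last visit at week 16.

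**The case against.** **The loss may be negligible.** Starting at week 5 suggests that later granulation was expected. If medians are 4 weeks or more, the figures above show almost no loss. The largest losses come from 2.5 v 4 weeks, where 98 to 99.9% and 86 to 94% of wounds would granulate by week 8, near the ceiling for the 8-week outcome. This stands as a limit on size. It does not remove the gap, because the form states no expected times and no reason for the late start.

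**Source material exists.** A photo is taken at every visit, and wound care happens at Visits 1 to 4. A reader might infer that early granulation is lost beyond recovery. The documents do not support that, since photos could partly date it. But the form names no reading of them for granulation, no reader and no rule.

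**Bias.** A reader might infer that the late start distorts the comparison or produces false positives. It does not materially inflate type I error, and differences in the proportion granulated by week 5 stay visible.

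**Other documents.** The form calls itself a reliance protocol, cites a protocol in Section S, and refers to a consent-form table for questionnaire timing. Neither was available, and a fuller schedule or a recurrence follow-up may be there. This stands, and limits both points to this form.

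**Recurrence.** Patients come largely from the co-investigators' own practices (Section J2), and Section K allows use of health records, so later recurrences could be found. No such check is named. A reader might also infer a biased rate ratio. If counts stopped at week 16 with no time-at-risk term, and healing medians were 8–9 v 11–14 weeks, the ratio at equal hazards would be 1.06 to 1.32. But Section G2 neither states nor excludes such a term, and Section D assumes comparable healing times, under which the ratio is 1.00. That bias is not established.

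**Conclusion.** The point holds as a loss of dating and precision for one primary outcome. As scheduled, events in weeks 1 to 4 merge into a single record at week 5, and no median before week 5 can be estimated.

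Its size depends on granulation times that the documents do not give. Under the Weibull assumptions it is slight at medians of 4 weeks or more, moderate at 3, and worth having back at 2.5, where intervals widen by 14 to 30% and power at 2.5 v 4 falls by 4 to 10 points. The 17 per group is unaffected.

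The recurrence mismatch is real but secondary: for wounds healed at week 8 or later, the listed visits cover less than a third of the stated window.

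**What to change.** 1. Record Granulation Assessment at Visits 1 to 4. State the criterion for successful granulation, which the form lacks, and use the same criterion at every visit as at week 8, so that any early red tissue is not counted as the event.
2. Define time to granulation as the first weekly visit that meets the criterion, and analyse it as weekly grouped time.
3. If granulation cannot be judged before week 5, say why, and analyse first records at week 5 as left-censored, meaning granulated by week 5.
4. Secondary: reconcile Sections F1, F2 and G2 on the recurrence window and its starting point. Either name a record check after week 16 or limit the window to week 16. Include log observed time since healing as an offset in the rate-ratio model.

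Cost: no new visits, but some extra time at four existing ones. Visit 5 is listed at 70 minutes and Visit 3 at 50, and Granulation Assessment is the only listed difference. Taken at face value, that is up to 4 × 20 = 80 minutes per patient, or about 45 hours for 34 patients and 67 for 50. This is indicative only: Visit 6 adds a thermal image to the Visit 5 items and is also listed at 70 minutes. Recurrence needs a wording change, plus one chart check per healed patient if the six-month window is kept.
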